**b. Data Analysis and Data Monitoring:**

Drs. [name] and [name] will conduct and/or supervise and have final responsibility for all analyses. Drs. [name] and [name] will conduct and/or supervise portions of the analysis that fall under their specific areas of expertise. Under the direction of the senior statistical team, [name], [name] and [name] will carry out portions of the programming and analysis, which will begin within 6 months of the start of the trial (see Milestones). Analysis of short-term data will be complete by month 68 (when the last patient will have been followed for six months), and analysis of the long-term data will be completed by month 69 (when all 24- month follow-up will be complete), which will allow graphical and tabular summaries and narrative interpretation of the results to be completed by Month 72. No interim efficacy analyses or adaptive features are planned. Model fitting performed before all outcome data are available will be provisional, for the purpose of verifying code and making limited modeling decisions (e.g., determining from early data whether parameters, such as residual variance or scale reliability, may vary among subgroups). The Data Management and Biostatistics Committee will receive regular updates on progress in completing the statistical analysis plan, discuss any additional or modified analyses, and report to the Steering Committee as necessary.

**Data Analyses:** MOBILITY will use REDCap for patient-reported outcomes. REDCap is a software toolset and workflow methodology for collection and management of clinical research data developed by Vanderbilt University, in collaboration with institutional partners including the University of Cincinnati Academic Health Center. This secure, flexible, web-based application provides: 1) an intuitive interface

for data entry and real time validation (e.g., automated data type and range checks); 2) HIPAA-compliant and 21 CFR Part 11-ready audit trails for tracking data manipulation and exports; 3) record locking and electronic signature functions; 4) control of view/edit rights; 5) a tool for reporting, monitoring and querying patient records; and 6) automated export to common statistical packages. REDCap is hosted on a network specially designed to support the rigorous security and compliance requirements of clinical research projects. Administered by the CCHMC Division of Biomedical Informatics, this network features multiple firewalls and a central facility for managing hosted systems and users, creating another layer of access control and audit capability on top of what REDCap already provides (e.g., user access can be monitored and controlled at the network level without making any changes within REDCap itself). These capabilities are available to authorized network administrators and REDCap study owners only, and user access changes are documented by an audit trail. The data management team will monitor the database throughout the study to assure that data are complete and accurate.

**Analyses of Specific Aims:** Each specific aim involves assessment of domains that are hypothesized to be affected by MET either directly or indirectly through other domains. Our approach to potential HTE distinguishes effect moderators from mediators of distal outcomes. Moderators include fixed patient characteristics and pre-treatment covariates values. Mediators include variables that are hypothesized to be affected by MET treatment and that may in turn affect other outcomes. We will utilize generalized linear mixed models (GLMM), which allow for outcomes from a range of distributions and will include random effects to account for unspecified causes of variation among sites and patients, and subgroup-specific coefficients to assess HTE.

The basic model for outcomes will be a GLMM with change from baseline to either 6- or 24- months as the dependent variable. Independent variables will include fixed-effect terms for randomized treatment group (MET), baseline value of the outcome, and random site effects. For HTE analyses, a baseline value-by-MET interaction (to assess HTE due to baseline status) will be included, and for particular domains additional continuous or categorical covariates and treatment-by-covariate interaction terms will be added to assess HTE. Outcomes within each domain will share the same set of HTE terms, specified in the Specific Aims. Because the subgroups are in general correlated (e.g., duration of SGA treatment, weight gain history and psychotropic weight burden will be correlated with baseline BMI), we will include multiple first-order HTE terms simultaneously (to assess heterogeneity independently attributable to each moderator), but will also fit separate models for each term to gauge the impact of this correlation on our conclusions. Higher-order treatment-by-covariate interactions will not be included a priori, but will be explored with rigorous adjustment for multiple testing, using step-down testing (removing highest-order interaction terms first) or information criteria based on penalized likelihoods to guide model selection.

**Marginal Structural Modeling for Causal Inference:** SA1 concerns the overall and sub-group specific effects of MET on abrogation of weight gain (with changes in BMI z-score from baseline as outcomes) and metabolic health, particularly metabolic syndrome and its component criteria. BMI and adherence measures are obtained at all study visits, so our models for these measures will use all available observations by treating the longitudinal series of changes in these variables and SGA treatment as dynamically dependent on each other. We will use marginal structural models to address this bi-directional dependence, computing the probability of SGA treatment regimen change at each visit within weight gain treatment regimen groups and using appropriately normalized versions of the inverse of the probability as the stabilized weights.

**Adjustment of Self-Reported Adherence:** Adherence rates for self-report and MEMS (where available) will be calculated as number of treatments/day divided by number of prescribed daily treatments. Truncated MEMs adherence rates (maximum of 100%) will be used in analyses to reduce inflation as a result of overuse or extra openings due to prescription refills. This method has been used successfully in studies assessing electronic monitoring (EM) adherence. Self-reported adherence vastly underestimates adherence as measured by EM. While it is not feasible to use EM for all patients and medications, we will use the statistical relationship between EM and self-reported adherence in a subsample of 300 patients (equal numbers per treatment group, i.e., 100 for SGA adherence who are also taking MET, 100 for SGA adherence who are not taking MET, and 100 for MET adherence, who are

randomly selected the 8 randomization strata) to estimate EM adherence from self-report in the remaining patients. We will regress EM adherence on self-reports, using standard diagnostics to ensure that non-linearity, heterogeneity of variance across the range of adherence, or subgroup-specific regression relationships are included as needed. Predictions that accurately reflect the residual uncertainty can then be generated by multiple imputation, and the resulting complete-sample datasets will be used in primary analyses involving SGA adherence, with sensitivity assessed by parallel analyses using self-report directly.

**Data and Safety Monitoring plan:** The Cincinnati site will provide an independent certified study data monitor who will visit each site prior to study initiation and approximately every 6 months thereafter. The monitor will follow a monitoring plan that includes source data verifying and ensuring compliance with good clinical practices (GCPs), the IRB-approved protocol and other applicable regulatory guidelines, and will report any problems to the site PI and the other clinical staff members. Additionally, adherence to inclusion/exclusion criteria, completion of scheduled assessments, withdrawal/termination procedures, and maintenance of training and certification for all research personnel will be continuously monitored. The monitor will provide written recommendations following each visit to each site. All reports will be reviewed by members of the Steering Committee.

Safety and tolerability data will be monitored by an independent Data Safety Monitoring Board (DSMB), the study investigators, and the CCHMC and NS/LIJ IRBs. The function of the DSMB is to protect the safety of the study participants. The DSMB members are: [name], pharmacoepidemiologist with focus on SGA risks; [name], adult diagnosed with BSD as an adolescent; [name], biostatistician; [name], child psychiatrist; [name], pediatric endocrinologist; and [name], parent of youth with BSD. Members will disclose and resolve any potential conflicts of interest prior to each meeting.

At their initial meeting (prior to study initiation), the DSMB members will select a Chair, who will provide written meeting minutes and recommendations and will review the study protocol and consent forms for safety and validity. Biannually, they will evaluate whether recruitment goals are being met and monitor the occurrence of adverse events and early withdrawals or terminations. All serious adverse events will be reported to the site's IRB and the DSMB within 7 days of knowledge of occurrence and will be followed until resolution, permanent outcome of the event, or stabilization. The DSMB will provide recommendations based on this review (e.g., to terminate the study or recommend modifications, including additional safety or tolerability measures). [name], in conjunction with the DSMB, will be responsible for ensuring that DSMB reports are filed with the IRBs and PCORI. The DSMB will also provide the investigator with a summary report that includes their recommendations. Adverse event reports will be collected systematically at patient visits, any rated as severe will be documented and reported. All adverse events will be reviewed by the DSMB biannually and reports will be sent to the FAC and Steering Committees.

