1. Patients will be excluded if they have had exposure to a total daily dose of MET 1000 mg bid for at least 2 weeks in the past 3 months;
2. Patients will be excluded if they could not tolerate MET during the recommended titration schedule outlined in the protocol;
3. Major neurological or medical illnesses that affect weight gain (e.g., unstable thyroid disease) or require a systemic medication that might impact weight or glucose regulation (e.g., diabetes mellitus [insulin], chronic renal failure [steroids]);
4. If lab results are available in the last 6 months, then a fasting serum glucose  $\geq 126 \text{ mg/dL}$  on two occasions prior to or during screening, indicating need for prompt treatment.
5. If lab results are available in the last 6 months, then a serum creatinine  $\geq 1.3 \text{ mg/dL}$  on two occasions during screening and/or follow-up, indicating potential impairment of renal functioning
6. Pregnant or breast feeding;
7. Based on their clinician's assessment, children and caregivers who are unable to complete screening/baseline assessments for any reason;

The enrollment rate will be approximately 1-2 patients/month/site for a recruitment time of 57 months.

**Randomization:** We will randomize 1800 patients (1:1 ratio) to either MET + LIFE or LIFE alone. All patients will receive a lifestyle intervention (LIFE) of brief standardized education. Once a patient is determined to meet the above criteria and has provided appropriate informed consent/assent, site staff will assign the participant a patient ID number. The site staff will then log on to the study's REDCap site and enter the Patient ID, and the following stratification factors: site, overweight or obese, previous SGA exposure, and sex of patient (transgendered patients will be randomized according to sex assigned at birth). REDCap has a built in mechanism that prevents duplication of subject ID numbers.

Once all stratification factors have been entered, the REDCap randomization module will return the next assignment for the appropriate strata.

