**d. Setting:** Assessments will be conducted at the participating community-based private and public mental health treatment centers in the East Coast and Midwest Regions. The participating site personnel will be made up of a real-world clinical trial team that includes members with varied training and experience with appropriate support from a qualified physician and centralized study trial team. Site staff who will be obtaining informed consent, reviewing medication lists, and collecting and assessing adverse events must complete Human Participants Protection and Good Clinical Practice (HPP and GCP) training prior to involvement in the study. These essential study staff will be documented via a site specific delegation of authority (DOA) log. DOA logs will be reviewed by the study monitor at each site visit to ensure that all new essential study staff have been added.

**e. Laboratory methods and facilities:** Participants will be sent for blood work, at the clinician's discretion, to any laboratory facility. No specific laboratory test will be mandated, as it is expected that laboratory procedures will take place in settings where everyday care happens, such as community clinics, hospitals and health systems. It is recommended that clinicians adhere to practice guidelines and labs are ordered through the patient's medical practice by their clinicians.

**f. Estimated Period of Time to Complete the Study:** The following is a timeline for the 72-month period of the proposed study: Months 1-2: Train study personnel; Months 3-57: Recruit an average of approximately 1-2 patients/site/month from 40 sites over 54 months for a total sample size of 1800 patients, we expect 25% of the sample recruited by M10-11; 50% recruited by M30; 75% by M45 and the final patient recruited by M57; Months 34-68: Complete subject participation, data entry, and analyses. Final analyses will be completed M70- after the last patients have completed 6 and 24 months of follow-up.

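### Last enrolment at study month 57 plus 24 months of follow-up gives about month 81, but the plan calls 24-month follow-up complete at months 69 to 70

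*Combined protocol and SAP*

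**What the plan says.** In what follows, M57 means study month 57, and month 24 means 24 months after a patient's own baseline.

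- **Recruitment.** Section E.f (Estimated Period of Time to Complete the Study) states: "Months 3-57: Recruit an average of approximately 1-2 patients/site/month from 40 sites over 54 months". It expects "75% by M45 and the final patient recruited by M57; Months 34-68: Complete subject participation, data entry, and analyses". Section E.a gives the rate "for a recruitment time of 57 months", and sections F.b and F.f also give 57 months.
- **Follow-up.** The Study Schedule and Treatment part of section E.a sets a total of 24 months per patient and describes the month 6 and month 24 data as primary outcomes.
- **Analysis dates.** Section E.b (Data Analysis and Data Monitoring) states: "Analysis of short-term data will be complete by month 68 (when the last patient will have been followed for six months". For the long-term data it states: "analysis of the long-term data will be completed by month 69 (when all 24- month follow-up will be complete". It expects the tables, graphs and "narrative interpretation of the results to be completed by Month 72".
- **Final analyses.** Section E.f states: "Final analyses will be completed M70- after the last patients have completed 6 and 24 months of follow-up". The same section gives the whole study 72 months.
- **Early fits.** Section E.b adds: "Model fitting performed before all outcome data are available will be provisional".

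**The concern.** A patient enrolled at M57 has been followed for 12 months at M69 and for 15 months at M72. The plan therefore claims complete 24-month follow-up at a time when its own recruitment schedule rules that out.

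This matters because month 24 is named as a primary time point and all three aims carry 24-month hypotheses. Sections E.b and E.f each attach a completion condition to their date. Date and condition cannot both be met, and the text does not say which gives way. One choice lengthens the study. The other removes the month-24 value for patients enrolled late.

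**Working it through.** **Inputs.** N = 1800 (section E.a, Randomization). Enrolment of 50% by M30, 75% by M45 and the last patient by M57 (section E.f). Follow-up of 24 months (study schedule). Stated dates: M68 for the end of participation, M69, M70, and M72 for the end of the study.

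**1. The plan's own figure.** All month-24 follow-up is complete at M69 only if the last patient enrols by 69 − 24 = M45. That is the 75% milestone, not the end of recruitment.

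**2. The date implied by M57.** 57 + 24 = M81. This is 81 − 69 = 12 months after M69, 81 − 70 = 11 after M70, and 81 − 72 = 9 after the end of the study.

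**3. The recruitment end.** Within section E.f, Months 3-57 and 54 months agree, since 57 − 3 = 54. The difference lies with the 57 months in sections E.a, F.b and F.f. Counted from month 3, 57 months end at M59 (first month counted inclusively) or M60 (elapsed months). The last month-24 visit is then at M83 or M84, which is 11 or 12 months past M72.

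**4. Shortfall if a date governs.** A patient reaches month 24 by cut C only if enrolled by C − 24. The M69 row uses the 75% milestone directly. The other rows assume linear accrual between milestones.

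| Cut | Enrolled by | Fraction f reaching month 24 | N = 1800f | Short | SE ratio 1/√f |
|---|---|---|---|---|---|
| M68 | M44 | 0.50 + 0.25 × 14/15 = 0.7333 | 1320 | 480 | 1.168 |
| M69 | M45 | 0.7500 | 1350 | 450 | 1.155 |
| M70 | M46 | 0.75 + 0.25 × 1/12 = 0.7708 | 1387.5 | 412.5 | 1.139 |
| M72 | M48 | 0.75 + 0.25 × 3/12 = 0.8125 | 1462.5 | 337.5 | 1.109 |

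If recruitment ends at M60, the M68 and M69 rows do not change. The shortfall becomes 1800 × (0.25 − 0.25 × 1/15) = 420 at M70 and 1800 × (0.25 − 0.25 × 3/15) = 360 at M72.

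**5. Allowing for dropout.** Section F.f expects about 90% retention over two years. Applied equally, that gives 0.9 × 1350 = 1215 at M69 against 0.9 × 1800 = 1620 with full follow-up. The ratio √(1620/1215) = 1.155 is unchanged. Both counts are optimistic, because the study schedule expects some visits to be missed.

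**6. Month 6.** 57 + 6 = M63, or M66 if enrolment ends at M60. Both fall before M68.

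**The case against.** The strongest reply is that nothing will be lost. Both long-term dates are tied to completion, section E.b treats earlier model fits as provisional, and no visible passage sets a database lock or an administrative cut-off. This stands in part. A reader might infer that the plan will forgo month-24 data on a quarter of its patients, and the documents do not support that. They leave the question open. The Milestones that section E.b refers to are not in the text supplied, so the absence of a cut-off rule is provisional. The dash after M70 may also be the remnant of a range.

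Visit times are approximate, but that cannot absorb 12 months. With an assumed early window of three months, 337.5 patients are still short at M69 (enrolled after M48). At M72 the figure is 1800 × (0.25 − 0.25 × 6/12) = 225. The remark in section G.a about monitoring for up to 24 months concerns patients who stop assigned treatment. It does not set shorter follow-up for late enrollees.

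Four other stronger readings should be resisted:

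- **That M68 and M69 in section E.b contradict each other.** Both are latest dates. A last patient enrolled by M45 would satisfy both. Only M69 conflicts, and it conflicts with M57.
- **That 25% is the maximum loss.** It is the figure at M69. At the M68 end of participation the loss is about 480 (26.7%).
- **That precision for BMI falls by the full 15%.** The basic model in section E.b uses change to month 24, for which the complete-case figure is apt. For BMI and adherence, however, the marginal structural modelling paragraph uses all available observations, and patients enrolled late would contribute values from months 12 to 21.
- **That the treatment comparison is biased.** Assignment is 1:1 and stratified by site, and a calendar cut does not depend on arm.

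**Conclusion.** The inconsistency is real and should be fixed. On the plan's own dates the last month-24 visit falls at about M81 (M83-M84 if 57 months are counted from month 3), not at M69 or M70, and not within 72 months.

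If the completion conditions govern, the cost is an overrun of about 9 months and no data. If the dates govern, 450 of 1800 patients cannot reach month 24 at M69. That number assumes only that the 75% milestone is met on time. The figures of about 480, 412 and 338 at M68, M70 and M72 also assume linear accrual.

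The 15% larger standard error applies to outcomes analysed only as change to month 24. It bears most on measures that Table 2 schedules only at baseline, 6 and 24 months, such as the PROMIS anxiety and anger forms and the weight-related quality-of-life scales. For these, a late enrollee's last value would be at month 6.

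**What to change.** Put sections E.b and E.f on one calendar. Reconcile 57 with 54 months of recruitment, and state whether the dates or the completion conditions govern the 24-month analysis. Then choose one of two options.

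- **A. Complete follow-up.** Set the 24-month data cut after the last month-24 visit, at about M81. The cost is about 9 months beyond M72, plus analysis time.
- **B. A calendar cut at M68-M72.** Delete the statements in sections E.b and E.f that all, or the last, patients will have completed 24 months. State the expected month-24 sample for the chosen cut: about 1320 to 1460 before dropout, and 1350 at M69. Report patients cut off by the calendar separately from dropouts for every month-24 outcome. Align the 24-month duration in the study schedule, and the $155 payment total in section H (3 × $25 + 8 × $10, which includes month 24), with what late enrollees will complete. The cost is wording, reporting and a smaller stated month-24 sample, with no new patients or visits.

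Neither option requires a change to the analysis models in section E.b.

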#### **A. SPECIFIC AIMS**

The specific aim of this study is to address the significant gap in the evidence base for metformin (MET) use in overweight and obese youth with Bipolar Spectrum Disorders (BSD).

The overall objective of this prospective, large, PRAGMATIC randomized trial is to study the impact of MET and healthy lifestyle intervention (LIFE) vs. LIFE alone on patient-centered outcomes of body weight, Second Generation Antipsychotics (SGA) adherence and satisfaction, psychiatric symptom burden (e.g. mood/anxiety), and quality of life (QoL). We will also examine metabolic outcomes.

**Specific Aim 1:** Assess the overall and subgroup-specific impact of MET+LIFE versus LIFE alone on short- (6mo) and long-term (24mo) **weight and metabolic health** in overweight and obese youth with BSD.

**H1.1:** Overall, assignment to treatment with MET will abrogate more weight gain and lead to fewer adverse metabolic outcomes than LIFE alone at 6 and 24 months.

**H1.2:** (Heterogeneity of Treatment Effects [HTE]): MET's effectiveness at abrogating weight gain and components of metabolic syndrome will vary with respect to the following factors (see Patient Population and Background for rationale and prior data): 1) Change in BMI z-score from SGA initiation to baseline (in patients already receiving SGA treatment); 2) Prior exposure to and duration of SGA treatment; 3) Baseline BMI z- score; 4) Baseline psychotropic weight burden (in SGA non-naïve patients; as defined in Measures below); 5) BSD as diagnosed by a structured interview; 6) Age; 7) Type of insurance (public/private); 8) Ethnicity (Hispanic/Non); 9) Baseline insulin resistance (HOMA-IR); 10) Race (African-American (AA) vs non-AA).

**Specific Aim 2:** Assess the overall and subgroup-specific impact of MET+LIFE vs. LIFE alone on short- (6mo) and long-term (24mo) **SGA adherence and treatment satisfaction**, including assessment of how these effects may be mediated by MET effects on weight gain.

**H2.1:** Overall, assignment to treatment with MET will lead to better SGA adherence and greater treatment satisfaction than LIFE alone after both 6 and 24 months.

**H2.2:** (HTE): MET effectiveness with regard to SGA adherence will vary with respect to: 1) Baseline weight acceptability; 2) Baseline psychotropic medication treatment acceptability; 3) Type of insurance (public/private).

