**H2.3:** The overall effects of MET treatment on SGA adherence will be mediated by degree of weight abrogation, and this relationship will be stronger among girls than boys. We anticipate a possibly complex relationship between abrogation of weight gain (associated with MET) and SGA adherence, because weight gain may also be avoided via SGA non-adherence (at the probable cost of sub-optimal psychiatric outcomes; see Specific Aim 3). A statistical framework (marginal structural models) to accommodate this possibility is described in the Statistical Analysis Plan.

**Specific Aim 3:** Assess the overall and subgroup-specific impact of MET+LIFE vs. LIFE alone on **psychiatric symptom burden, psychotropic treatment changes, and overall and weight-related QoL**, including assessment of how these effects are mediated by MET effects on weight gain and SGA adherence.

**H3.1:** Overall, assignment to treatment with MET will be associated with lower psychiatric symptom burden, decreased risk for symptom-driven treatment changes, and greater improvements in overall and weight-related QoL than LIFE alone at both 6 and 24 months, post-randomization.

**H3.2:** (HTE): MET effects on psychiatric symptoms will be smaller in patients who meet full DSM criteria for a BSD.

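### The plan does not say which BMI z-score analysis tests H1.1 or what it assumes about missing BMI, and its analytic-group rule and its dates conflict with a randomised month-24 comparison

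*Combined protocol and SAP*

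**What the plan says.** **Hypothesis.** H1.1 (section A) says "assignment to treatment with MET will abrogate more weight gain" than LIFE alone, at 6 and 24 months. BMI z-score is the primary outcome.

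**Change-score model.** Section E.b, Analyses of Specific Aims, plans mixed models that "will include random effects to account for unspecified causes of variation among sites and patients". It then says: "The basic model for outcomes will be a GLMM with change from baseline to either 6- or 24- months as the dependent variable". The terms are randomised group, baseline value and random site.

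**All-visit model.** The next paragraph of E.b, on marginal structural modelling, opens with Aim 1 and change in BMI z-score. Because BMI and adherence are recorded at every visit, "our models for these measures will use all available observations by treating the longitudinal series of changes". The weights come from "computing the probability of SGA treatment regimen change at each visit within weight gain treatment regimen groups". Section A introduces this method under H2.3, the mediation hypothesis: "A statistical framework (marginal structural models) to accommodate this possibility is described in the Statistical Analysis Plan".

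**Analytic group.** Section E.a, Study Schedule and Treatment, lets clinicians start or continue metformin at their discretion after a recommended initial period. It assigns those patients' data to a separate analytic group, whatever arm they were randomised to.

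**Missing data.** E.a expects incomplete visits and stresses months 6 and 24. F.f expects about 90% retention over two years. The only imputation described (E.b) is for adherence. A missing-data paper is listed as reference 155, but the available text does not cite it.

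**Dates.** E.b: "analysis of the long-term data will be completed by month 69 (when all 24- month follow-up will be complete"). E.f (Estimated Period of Time): "75% by M45 and the final patient recruited by M57", with final analyses at M70 after the last patients' 24-month follow-up, in a 72-month study.

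**The concern.** The two BMI analyses can differ in which patients count and in what is estimated. A change score at month 24 uses only patients seen then. An all-visit model also uses those with earlier BMI. Weights for SGA regimen change concern a variable that arises after randomisation. They suit a question about mediation or a controlled SGA regimen, but the effect of assignment does not need them. If neither analysis is designated, the H1.1 result can rest on a choice made once data are visible, in a trial where no placebo is described.

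The analytic-group rule matters more in principle. Applied to H1.1, it would define groups by what clinicians did after randomisation, so the comparison would no longer be randomised.

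The dates bear on the same question, because they determine how many patients the month-24 change score could use.

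**Working it through.** **1. Which analysis tests H1.1?** Set side by side:

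- For the all-visit model: the paragraph that names BMI z-score assigns BMI to it, and random patient effects fit repeated measures.
- For the change score: it is the stated basic model, it uses randomised group, and its time points are those of H1.1.
- Neither is called primary, supportive or sensitivity in E.b, and H1.1 is not mentioned there.
- The all-visit description does not say whether SGA change is a term in the outcome model, or how the month-6 and month-24 contrasts are obtained.

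So a BMI model is described, but its designation and the effect it targets are not settled.

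**2. Dates.** Last enrolment implied by each statement:

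- E.b, all 24-month follow-up complete at month 69: 69 − 24 = M45.
- E.b, last patient's six-month point at month 68: 68 − 6 = M62.
- E.f, stated directly: M57, so the last 24-month visit is at 57 + 24 = M81, past month 72.

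Share unable to reach month 24, interpolating linearly between E.f's 50% at M30, 75% at M45 and 100% at M57:

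| Cut-off | Enrolled by | Recruited | Cannot reach month 24 |
|---|---|---|---|
| M68 | M44 | 50 + 25 × 14/15 = 73.3% | 26.7% (480) |
| M69 | M45 | 75% | 25% (450) |
| M70 | M46 | 75 + 25 × 1/12 = 77.1% | 22.9% (about 412) |
| M72 | M48 | 75 + 25 × 3/12 = 81.25% | 18.75% (about 338) |

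At M69 each late recruit could still have at least 69 − 57 = 12 months of BMI.

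**3. Precision at month 24.** The plan gives no SD or power inputs to reproduce. Assumed: SD of change 0.5 (section C pilot, where the printed 0.27+0.5 is read as mean ± SD), equal at all ten post-baseline visits; correlation ρ^(months apart/3) with ρ = 0.85 or 0.95; random misses; 10% drop-out (F.f) spread evenly over visits; late recruits last seen at month 12, 15, 18 or 21 in equal shares.

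- Change score: n per arm = 900 × 0.75 × 0.90 = 607.5; SE = 0.5 × √(2/607.5) = 0.0287.
- All-visit model by generalised least squares with known covariance: sum, over last-visit patterns, the number of patients times the inverse covariance of the visits seen; invert; take the month-24 diagonal element V; SE = √(2V). Result: 0.0265 (ρ = 0.85) or 0.0250 (ρ = 0.95).
- Ratio: 1.08 or 1.15.
- Without the timeline loss, n = 810 per arm: 0.02485 against 0.02452 or 0.02411, ratio 1.01 or 1.03.

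The SD cancels from these ratios.

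Power (normal approximation, two-sided 5% assumed), taking the 24-week difference in the earlier three-arm trial (section C), −0.088 − 0.040 = −0.128, and carrying it to month 24: change score Φ(0.128/0.0287 − 1.96) = 99.4%; all-visit above 99.7%. At half that effect, 61% against 67-73% with the timeline loss, and 73% against 74-76% without it.

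**4. Bias.** It is zero if misses are random. Otherwise it depends on who leaves and in which arm, which the documents do not give. Drop-out in the earlier trial was 28% of 44 controls and 24% of 46 on metformin, about 12 against 11 patients (Fisher p = 0.81).

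**5. SGA weighting.** In simulation with assumed switching (18-53% of patients) and no missing data, weighting alone moved the estimate by −0.4% to +1.5%; adding SGA change as a model term moved it by 1-7%.

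**The case against.** The strongest reply is that E.b runs from general to specific: the basic model is a default, and BMI is expressly sent to the all-visit model. Emphasis on months 6 and 24 names time points, which an all-visit model also yields. This largely stands, and a reader who inferred that the plan is silent on how BMI will be modelled, or evenly split, would go too far. But this reading puts SGA-change weights into a test of assignment and still states no missing-data assumption. Using all available observations says which data enter, not what is assumed about the rest.

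Second, both E.b and E.f intend full 24-month follow-up. A reader might infer that a quarter of patients will certainly be lost at month 24. The documents do not support that: they contain dates that cannot all be true, and the loss follows only if the accrual dates are the ones that hold. Nearly all of the precision cost depends on this.

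Third, a reader might infer bias from weight gainers leaving the LIFE arm. The earlier trial's drop-out figures do not show a difference between arms, so any bias figure would rest on an invented mechanism.

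Fourth, the basic model omits sex and previous SGA exposure, two stratification factors. A reader might expect a measurable loss of precision, but the documents give no variance share for them, and BMI z-score is already standardised for sex.

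**Conclusion.** The point holds as a fault of designation and consistency. E.b leans to the all-visit weighted model for BMI but does not name the H1.1 test or state a missing-data assumption. The analytic-group rule in E.a conflicts with the randomised group in E.b and would break the randomised comparison if used for H1.1. The dates in E.b and E.f cannot be reconciled as written.

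The numerical consequence is moderate and doubly conditional: it needs both the accrual dates and the change score, and it rests on the assumed correlation and drop-out pattern. A claim that the trial is underpowered is not supported: on the assumed inputs, power at the earlier trial's effect is above 99% either way. Confidence is high on the textual conflicts and lower on the magnitudes.

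**What to change.** - **Name the H1.1 analysis:** an unweighted repeated-measures mixed model of BMI z-score change at all post-baseline visits, every patient in the randomised arm, with baseline BMI z-score, sex, previous SGA exposure and random site. Read the month-6 and month-24 contrasts from it. Other all-visit models by assigned arm could serve; what matters is that one is fixed in advance.
- **State the missing-at-random assumption** for BMI and add one sensitivity analysis for misses that depend on unseen BMI.
- **Keep the SGA-weighted marginal structural model** for H2.3 and as a supportive analysis of BMI.
- **Use the analytic group** for clinician-started metformin only in a supportive analysis, and reconcile that passage of E.a with E.b.
- **Reconcile the dates** in E.b and E.f, and say how patients not yet at month 24 enter the month-24 contrast.

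Cost: SAP wording and a little more programming; no new data. The downside is reliance on missing-at-random given observed BMI and, for late recruits, on date of enrolment being unrelated to the treatment effect.
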